5.4.2.3 TTR

The analysis of TTR will be based mainly on the FAS. Only subjects with confirmed tumor response (CR or PR) are descriptively summarized by treatment group.

TTR (months) is calculated as: (date of the first documented CR or PR – date of the first dose +1) / 30.4375.

5.4.2.4 DoR

DoR will only be analyzed for subjects with confirmed tumor response (CR or PR) after treatment. The censoring rules for DoR are the same as those for PFS, and the end date of response must be consistent with the date of progressive disease or death of the PFS. For DoR, the Kaplan-Meier product-limit approach will be used to calculate the median survival by treatment group, the corresponding 95% confidence interval (CI) will be calculated using the Brookmeyer-Crowley method based on log-log transformation, and the survival curves will be plotted.

DoR (months) is calculated as: (date of PFS event – date of the first documented CR or PR + 1) / 30.4375.

5.4.2.5 Immunogenicity evaluation

Immunogenicity analysis will be based on the ADAS.

The ADA will be statistically analyzed using descriptive statistics in the form of listing based on the confirmatory results of immunogenicity.

The numbers and percentages of subjects who are non-treatment emergent ADA positive, treatment-enhanced ADA positive, treatment-induced ADA positive, ADA positive, and ADA negative will be summarized.

In treatment-induced ADA positive subjects, the time when first tested positive, as well as the number and percentage of transiently positive, persistently positive, and other positive subjects after baseline will be summarized.

Also, the number and percentage of neutralizing antibody (Nab) positive and negative subjects will be summarized.

The classification of immunogenicity is as follows:

- (1) Non-treatment emergent ADA positive includes two situations: (a) positive at baseline and negative after baseline; (b) positive at baseline and positive after baseline, with a titer $< 4 \times$ that of the baseline ADA positive sample.
- (2) Treatment-enhanced ADA positive: positive at baseline and positive after baseline, with a titer $\geq 4 \times$ that of the baseline ADA positive sample; treatment-induced ADA positive: negative at baseline and positive after baseline; ADA positive: including treatment-enhanced ADA positive as well as treatment-induced ADA positive. Situations other than ADA positive are regarded as ADA negative.
- (3) Transiently positive refers to negative at baseline and with ADA positive for only once that is not persistent after baseline to the time before the last test.

Persistently positive consists of two categories: (a) negative at baseline but with at least 2 post-baseline samples, with the interval between the first and last positive samples more than 16 weeks; (b) negative at baseline but with last post-baseline sample tested positive, or with the last post-baseline sample negative and the penultimate post-baseline sample tested positive.

"Other" refers to negative at baseline, with at least two ADA-positive samples but not persistently positive and with negative last sample.

- (4) Nab positive: negative at baseline and positive after baseline; Nab negative: negative after baseline; all other circumstances are classified as indeterminable.

5.4.3 Exploratory analyses

PD-L1 expression will be analyzed using descriptive statistics based on the TMKS.

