5 STUDY POPULATION

5.1 Inclusion Criteria

Patients must meet all of the following inclusion criteria to be eligible for this study.

1. All patients must sign an ICF prior to starting any study-related procedures
2. Aged ≥ 18 and ≤ 70 years
3. Histologically or cytologically confirmed small cell lung cancer
4. Staged ED-SCLC according to VALG staging
5. Have previously received first-line platinum-based treatment for ED-SCLC and have shown objective imaging progression. Including:
 - Sensitive recurrence: progression in ≥ 90 days from the last chemotherapy
 - Drug-resistant recurrence: progression during chemotherapy or within 90 days from the last chemotherapy
6. Able to provide tumor tissue samples for diagnosis, either archived samples within 12 months prior to the first dose of study drug or freshly obtained. The specimens shall meet the requirements of formalin-fixed and paraffin-embedded (FFPE) tumor tissue blocks allowing the cutting of at least 5-10 slices with a thickness of 4-6 μm for staining and testing. Cell smears from fine needle aspiration or centrifuged pleural fluid, bone lesions without soft tissue components or decalcified bone tumor specimens, and drill biopsy tissues are not acceptable, as they are insufficient for biomarker detection
7. ECOG PS of 0-1
8. Life expectancy of ≥ 8 weeks
9. With at least one target lesion without previous radiotherapy (RECIST v1.1) shown by CT or MRI scan ≤ 28 days prior to the first dose of study drug
10. Males and females of reproductive potential must take contraceptive measures from the first dose of study drug to within 24 weeks after the last dose of study drug (see 6.6.2 of the protocol for recommended contraceptive methods)
11. Had no transfusion of blood or blood products within 14 days prior to the first dose, not corrected with G-CSF or other hematopoietic colony-stimulating factors. Before the first dose of study drug, laboratory test values must meet the following conditions:
 - (1) Hematology: $\text{WBC} \geq 3.0 \times 10^9/\text{L}$; $\text{ANC} \geq 1.5 \times 10^9/\text{L}$; $\text{PLT} \geq 100 \times 10^9/\text{L}$; $\text{HGB} \geq 9.0 \text{ g/dL}$

- (2) Liver function: AST $\leq 2.5 \times$ ULN, ALT $\leq 2.5 \times$ ULN for patients without liver metastasis; ALT and AST $< 5 \times$ ULN for patients with liver metastasis; TBIL $\leq 1.5 \times$ ULN (TBIL < 3.0 mg/dL in patients with Gilbert syndrome); and ALB ≥ 3 g/dL

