8.6 Biomarker Analysis

Subject to the permission of the ethics committee, all subjects who meet the inclusion criteria shall provide diagnostic tumor tissues at baseline. Acceptable tumor tissues include 5-10 unstained 4-6 μ m slices prepared with archived tumor tissues or freshly obtained during the screening period.

After the subject's ICF is obtained and after the study medication, another biopsy is preformed before PD or treatment discontinuation to provide tumor tissue to the central laboratory for testing and analysis of the relationship between the change in PD-L1 expression before and after the administration and the efficacy. These samples may also be used for exploratory biomarker analysis, including but not limited to PD-L1 expression.

After the subject's ICF is obtained, about 16 mL of peripheral blood may be collected for tumor biomarker detection during the screening period, at each tumor evaluation, and the end of the treatment.

Refer to the Laboratory Manual for sample processing, handling, and transportation.

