10.4 Analysis Sets

The analysis sets in this study include:

Full analysis set (FAS): an analysis set determined based on the intent-to-treat principle. This analysis set includes all subjects who have been randomized and have received at least one dose of the study drug. In the FAS-based analysis, subjects will be analyzed by groups after randomization (regardless of the actual treatment they receive).

Per-protocol set (PPS): a subset of the FAS. Subjects with protocol violations that are judged to have a significant effect on the efficacy will be excluded from this set. The list of subjects included into or excluded from the PPS should be reviewed and determined by the sponsor and the investigator before the database is locked.

Evaluable set (ES): a subset of the FAS, defined as the all enrolled subjects receive at least one dose of the study drugs and receive post-baseline tumor assessment at least once.

Safety set (SS): All subjects who have been randomized and have received at least one dose of the study drug. Analyses based on the safety set will be carried out according to the actual treatment received by the subjects.

ADA set (ADAS): All enrolled subjects who have received at least one dose of the study drug and have baseline and at least one post-baseline ADA evaluation data.

Tumor biomarkers set (TMKS): Subjects who have been randomized and received at least one dose of the study drugs, and have tumor biopsy samples make up the PD-L1 or TMB set.

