10.5.5 Exploratory analysis

The expression levels of PD-L1 and TMB will be analyzed using descriptive statistics. The analysis will be based on the TMKS.

The immunogenicity will be analyzed using descriptive statistics. The analysis will be based on the ADAS.

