2.2.3 Exploratory objective

- To evaluate the correlation between biomarkers (including but not limited to PD-L1 and TMB) and efficacy

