4.3 Exploratory Endpoint

- Tumor biomarkers (including but not limited to expression levels of PD-L1 and TMB in tumor samples)

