5 STATISTICAL ANALYSIS

5.1 General Considerations

5.1.1 Analysis sets

The analysis sets in this study included:

Full analysis set (FAS): an analysis set determined based on the intent-to-treat principle. This analysis set includes all enrolled subjects who have received at least one dose of the study drug. Based on the FAS, the subjects will be analyzed according to their scheduled doses.

Per-protocol set (PPS): a subset of the FAS. Subjects with major protocol violations that have a major effect on the study results will be excluded from this set. The list of subjects included into or excluded from the PPS should be reviewed and determined by the sponsor and the investigator before the database is locked.

Safety set (SS): all subjects who have received at least one dose of the study drug and underwent post-administration safety evaluation. Analyses based on the safety set will be carried out according to the actual treatment received by the subjects.

ADA set (ADAS): All enrolled subjects who have received at least one dose of the study drug and have baseline and at least one post-baseline ADA evaluation data.

Tumor biomarkers set (TMKS): all enrolled subjects who have received at least one dose of the study drug and have tumor biopsy samples (including peripheral blood) make up the PD-L1 or TMB set.

Table X. Analysis sets and corresponding endpoints

Endpoint	Analysis Sets				
	FAS	PPS	SS	ADAS	TMKS
Safety Endpoints	X				
ORR	X	X			
OS and 6/12-month OS rates	X				
PFS	X				
TTR	X				
DoR	X				
DCR	X				
Immunogenicity Evaluation				X	
Tumor Biomarkers					X

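### The exploratory objective relates PD-L1 and TMB to efficacy, but neither protocol 10.5.5 nor SAP 5.4.3 crosses a biomarker with an outcome, and SAP 5.4.3 omits TMB

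*SAP*

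**What the plan says.** The exploratory objective is the same in both documents (protocol 3.1.3, SAP 2.2.3): "To evaluate the correlation between biomarkers (including but not limited to PD-L1 and TMB) and efficacy". The exploratory endpoint (protocol 3.2.3, SAP 4.3) is the level of these markers, with PD-L1 and TMB both named and tumour samples as the source.

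Protocol 8.6 goes further. It gives the purpose of a second biopsy, taken with consent after study medication, as "analysis of the relationship between the change in PD-L1 expression before and after the administration and the efficacy".

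The analysis sections are short. Protocol 10.5.5: "The expression levels of PD-L1 and TMB will be analyzed using descriptive statistics". SAP 5.4.3, in full: "PD-L1 expression will be analyzed using descriptive statistics based on the TMKS".

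The tumour biomarker set (TMKS) differs between the documents. In protocol 10.4 it is treated, randomized subjects who "have tumor biopsy samples make up the PD-L1 or TMB set". In SAP 5.1.1 it is treated, enrolled subjects who "have tumor biopsy samples (including peripheral blood) make up the PD-L1 or TMB set".

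**The concern.** The objective concerns a relation between two variables, whereas the planned analysis describes one of them. A summary of PD-L1 values, however complete, says nothing about whether subjects with higher values respond more often or live longer.

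What is at stake is the use made of the samples. Tissue is a condition of entry, a second biopsy may be requested, and about 16 mL of blood may be drawn at each tumour evaluation. If the analysis is not laid down in advance, any association that is reported will rest on cut-offs and outcomes that could have been chosen after the results were seen. A reader could not tell a planned finding from a selected one.

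**Working it through.** The documents give no sample size, cut-off or effect size for the biomarker objective, so there is no stated figure to reproduce. The check compares sections and then gives an illustration of scale.

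**Step 1: is a biomarker crossed with an outcome anywhere?**

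| Section | Biomarker named | Efficacy outcome in the biomarker analysis |
|---|---|---|
| Protocol 3.1.3, SAP 2.2.3 (objective) | PD-L1, TMB | Yes, by intent |
| Protocol 8.6 (biopsy purpose) | Change in PD-L1 | Yes, by intent |
| Protocol 10.5.5 (analysis) | PD-L1, TMB | None |
| SAP 5.4.3 (analysis) | PD-L1 only | None |
| SAP 5.1.4 and 5.4.4 (covariates, subgroups) | None | Not applicable; split only by sensitive or drug-resistant recurrence |
| SAP 5.4.1 and 5.4.2.1 to 5.4.2.4 (BOR, ORR, DCR, OS, PFS, TTR, DoR) | None | Not applicable |

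Protocol 10.5.6 leaves further subgroups to the SAP. SAP 5.4.4 adds outcomes (OS, PFS, OS rates) but no biomarker subgroup. Intent is stated in the objective and in 8.6, and no analysis carries it out.

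**Step 2: TMB.** It appears in the SAP objective (2.2.3), endpoint (4.3) and TMKS definition (5.1.1). It is absent from the one sentence of analysis (5.4.3), although protocol 10.5.5 plans its description.

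**Step 3: what the missing table would show (illustration).** Inputs:
- PD-L1 positivity in SCLC of 28.6%, from protocol Table 3, a background table that states no cut-off.
- 45 subjects on the selected regimen (6 in Stage I + 39 in Stage II), or 57 over all regimens (18 + 39), from protocol sections 4 and 10.1.
- Assumed here: every subject has a result, and ORR is about 30% in both PD-L1 groups.

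The 95% Clopper-Pearson limits for x responders of n are the 2.5% quantile of Beta(x, n−x+1) and the 97.5% quantile of Beta(x+1, n−x).

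- N = 45: 0.286 × 45 = 12.9, so 13 positive and 32 negative. 4/13 = 30.8%, CI 9.1-61.4%. 10/32 = 31.3%, CI 16.1-50.0%.
- N = 57: 0.286 × 57 = 16.3, so 16 positive and 41 negative. 5/16 = 31.3%, CI 11-59%. 12/41 = 29.3%, CI 16-46%.

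**Step 4: ability to see a difference.** Assume an ORR of 50% in positives and 20% in negatives, with a two-sided 0.05 normal approximation.
- N = 45: pooled rate (6.5 + 6.4)/45 = 0.287; null SE 0.149; alternative SE √(0.25/13 + 0.16/32) = 0.156; z = (0.30 − 1.96 × 0.149)/0.156 ≈ 0.05; power about 52%.
- N = 57: the same steps with 16 and 41 give null SE 0.133, alternative SE 0.140, z ≈ 0.28; power about 61%.

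The table is feasible but imprecise. It can show a large difference and cannot exclude a moderate one.

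**The case against.** The objective is exploratory, and nothing in it touches the ORR rule, the sample size, safety or the choice of regimen. That stands and limits the weight of the point. It might also be said that descriptive statistics could be broken down by response. Neither text says so, and the SAP is where the protocol places its detailed methods.

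Three stronger readings are tempting, and the documents do not support them.

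- **That blood-only subjects spoil the analysis.** The SAP wording does let blood qualify a subject for the set. But inclusion criterion 6 requires subjects to be "Able to provide tumor tissue samples for diagnosis", the schedule of activities marks screening tissue as required, and blood is the optional sample. A subject with blood alone should be rare and would normally be a protocol deviation. The phrase naming a PD-L1 or TMB set can also be read as two marker-specific sets, and nothing says that missing PD-L1 values enter a denominator. The wording is loose, but it does not cause the gap.
- **That the SAP has abandoned TMB.** TMB remains in its objective, endpoint and set definition. Only the analysis sentence lacks it.
- **That the SAP alone departed from the protocol.** The missing link to efficacy is already in protocol 10.5.5. What is new in the SAP is the loss of TMB from the analysis and the blood wording.

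Two practical cautions also stand. Neither document gives a PD-L1 assay, score or threshold for this trial, so simply asking for positive versus negative would leave the cut-off open. And subjects give 5-10 slices, of which at least 5 are for PD-L1, so a subject who gives 5 may have none left for tissue TMB.

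**Conclusion.** The point holds. Both documents promise a biomarker-efficacy relation, protocol 8.6 adds a relation for change in PD-L1, and neither analysis section contains one. SAP 5.4.3 also falls short of protocol 10.5.5 by omitting TMB. Carried out exactly as written, the planned analysis leaves the exploratory objective unanswered. This is a contradiction between objective and analysis, and more than a lack of detail.

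Its reach is limited to that objective. A reader should not infer that the primary ORR conclusion is in doubt. The intervals above rest on an assumed 28.6% positivity, complete results and equal response rates, and they serve only to show scale: with 13 to 16 positive subjects, the estimate in that group would span roughly 50 percentage points. How many paired biopsies will exist cannot be worked out from the documents, because the second biopsy is optional.

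**What to change.** Amend SAP 5.4.3, and align protocol 10.5.5 with it:

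1. Restore TMB to the analysis.
2. Tabulate ORR with Clopper-Pearson 95% CI, and give Kaplan-Meier PFS and OS, by PD-L1 category and by TMB (for example, at or above versus below the median).
3. State the PD-L1 assay, score and cut-off, and the TMB split, before database lock.
4. Add the section 8.6 summary of PD-L1 change against efficacy for subjects with paired biopsies, and report how many pairs there are.
5. Base each analysis on subjects with an evaluable result for that marker, and report how many lack one.
6. As a minor clean-up, take the mention of peripheral blood out of the tissue PD-L1 set in SAP 5.1.1. If blood markers are to be analysed, give them their own set.

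The cost is a few more exploratory tables, with wide intervals that should be labelled as such. The PD-L1 tables need only samples and outcomes that the trial already plans to collect. Tissue TMB may be missing for subjects who supply only enough slices for PD-L1, so that table may rest on fewer subjects.

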5.4.4 Subgroup analysis

Based on the FAS, the following subgroup analyses will be performed on the primary efficacy endpoint ORR, as well as the secondary endpoints OS, PFS, and 6/12-month OS rates:

- Sensitive recurrence: progress in \geq 90 days from the last chemotherapy
- Drug-resistant recurrence: progress during chemotherapy or within 90 days from the last chemotherapy

5.5 Safety Analysis

Unless otherwise specified, the safety statistical analysis will be summarized and tabulated by the treatment group. All safety analyses will be conducted based on the SS. Normal and abnormal parameters for safety evaluation will be summarized based on scheduled and unscheduled visits. Single unscheduled examinations will only be listed.

5.5.1 Adverse events

Adverse events (AEs) will be analyzed based on the treatment-emergent adverse events (TEAEs):

- 1) All AEs that occur from the first study dose to 90 days after the last dose;
- 2) An AE that starts before the first study dose but worsens after administration.

Treatment-related AEs are defined as TEAEs with a causality of definitely related, possibly related, or indeterminable. If the relationship between an AE and the study drug is missing, the AE will be considered as a treatment-related AE.

All AEs will be coded with MedDRA 21.0. and graded by NCI-CTCAE v4.03. For the same SOC and/or PT, multiple cases of the same events that occur in one subject will be counted only once. For the same AE reported in one subject multiple times but varying in CTCAE grade, the AE of the greatest grade will be enumerated.

The incidence of AEs will be sorted from high to low based on their corresponding SOC in the SHR-1210 200 mg, IV, Q2W + apatinib 375 mg (or apatinib 250 mg), PO, QD group. The incidence of AEs in each SOC will be sorted from high to low based on their PT. If the incidences of \geq 2 PTs are equal, the AEs will be sorted alphabetically. If there is no AE under a SOC or PT, then analysis is not conducted.

The number of TEAE cases as well as the number of subjects based on the SS will be summarized in a table by dose group. The summary table should at least include the number of subjects with at least one TEAE/SAE/, TEAEs leading to treatment discontinuation, TEAEs leading to dose interruption or dose reduction, SAEs, SAEs leading to death, TEAEs of special interest, immune-related TEAEs (irAEs), and CTCAE grading. For all categories included in the summary table, CTCAE Grade ≥ 3 TEAEs and treatment-related AEs with an incidence of $\geq 5\%$ will be summarized by SOC and PT, respectively. Laboratory abnormalities with an incidence of $\geq 10\%$ will be summarized. TEAEs leading to treatment discontinuation, TEAEs leading to dose interruption or dose reduction, and all treatment-related AEs will be analyzed respectively for SHR-1210 and apatinib. An immune-related AE is determined in the case of an indeterminable immune-related AE.

In particular, the incidences and outcomes of AEs assessed per the CTCAE 4.03 below are separately analyzed:

- Hematologic toxicity
 - Grade 4, or
 - Grade ≥ 3 thrombocytopenia with hemorrhage, or
 - Grade ≥ 4 neutropenia with pyrexia and infection
- Grade ≥ 3 non-hematologic toxicity (except for laboratory abnormalities), hypertension, rash, diarrhea, nausea and vomiting that cannot be controlled after symptomatic treatment
- Grade ≥ 3 laboratory abnormalities that lead to medical interventions or hospitalization, or last for ≥ 7 days
- Any Grade 5 TEAE

The following protocol-specified AEs of special interest will be summarized by SOC and PT:

- Grade ≥ 3 infusion reaction
- Other Grade ≥ 3 immune-related adverse events (irAEs)

For reactive capillary endothelial proliferation, the collected patient information will also be listed.

Important TEAEs will be summarized by SOC and PT. Important TEAEs are defined as:

- Any TEAE leading to interruption or permanent discontinuation of SHR-1210 or apatinib
- Any TEAE leading to dose reduction of SHR-1210
- Any targeted treatment with concomitant medication, i.e., TEAE with corrective treatment

All AEs (including non-TEAEs) are listed.

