6.4.2 Apatinib

Dose interruption of apatinib is allowed for up to 4 weeks (from the actual time of last dose); otherwise the treatment of apatinib shall be discontinued. A maximum of one dose modification is allowed; otherwise the subject will be considered intolerable and the treatment of apatinib shall be discontinued. Refer to [Table 7](#) for the requirements of dose modification of apatinib.

Table 7. Requirements of dose modification of apatinib

Adverse Drug Reaction	Grade	Whether to Interrupt Treatment	Rules for Dose Modification
Hematologic	Grade 1-2	No	—
	Grade 3	Yes	
• For the first occurrence, interrupt the treatment until the adverse drug reactions recover to Grade ≤ 2, and resume the treatment at the original dose• For the second occurrence, interrupt the treatment until the adverse drug reactions recover to Grade ≤ 2, and resume the treatment at a reduced dose of 250 mg/d• For recurrence after dose reduction, the investigator should evaluate the risks/benefits of the continued apatinib treatment and determine whether the drug should be permanently discontinued

Adverse Drug Reaction	Grade	Whether to Interrupt Treatment	Rules for Dose Modification
	Grade 4	Yes	
Resume the treatment at a reduced dose of 250 mg/d after the adverse drug reactions recover to Grade ≤ 2For the recurrence of Grade 4 toxicity after dose reduction, the treatment shall be permanently discontinued
Non-Hematological	Grade 1	No	—
	Grade 2 (lasting for ≥ 7 d)	Yes	
Resume the treatment at the original dose after the adverse drug reactions recover to Grade ≤ 1
	Grade 3	Yes	
For the first occurrence, interrupt the treatment until the adverse drug reactions recover to Grade ≤ 1, and resume the treatment at the original doseFor the second occurrence, interrupt the treatment until the adverse drug reactions recover to Grade ≤ 1, and resume the treatment at a reduced dose of 250 mg/dFor recurrence after dose reduction, the investigator should evaluate the risks/benefits of the continued apatinib treatment and determine whether the drug should be permanently discontinued
	Grade 4	Yes	
Resume the treatment at a reduced dose of 250 mg/d after the adverse drug reactions recover to Grade ≤ 1For the recurrence of Grade 4 toxicity after dose reduction, the treatment shall be permanently discontinued

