- Grade 3: Second-stage hypertension (systolic blood pressure of ≥ 160 mmHg, diastolic blood pressure of ≥ 100 mmHg), more than one antihypertensive drug or a higher intensity treatment are required. For persistent or symptomatic hypertension, apatinib treatment should be interrupted; if hypertension is still uncontrollable after 4 weeks of treatment, apatinib treatment should be permanently discontinued.
- Grade 4: Life-threatening (malignant hypertension or persistent nerve damage, hypertensive crisis) emergency intervention, life-threatening (such as hypertensive crisis). For Grade 4 hypertension, apatinib treatment should be permanently discontinued. The dose of antihypertensive drugs used should be recorded at each visit.

The dose of antihypertensive drugs used should be recorded at each subject visit of the subjects. If hypertension still persists when the treatment is discontinued, blood pressure and the use of antihypertensive drugs should be monitored every 3 months until the blood pressure returns to normal or the study completion.

Reversible posterior leukoencephalopathy syndrome (RPLS)

Symptoms and signs consistent with RPLS are rarely reported in subjects receiving the drug treatment. This is a rare neurological disease. The symptoms and signs are: epilepsy, headache, mental status changes, visual disturbance, or cortical blindness, with or without hypertension. Once a subject develops RPLS, apatinib treatment should be permanently discontinued.

Proteinuria

Follow the schedule of study procedures for urinalysis, if:

- < 2+, continue the administration of apatinib as planned, no additional tests are required
- $\geq 2+$, immediately monitor the 24-hour urine protein. 24-hour urine protein:
 - < 1 g, continue apatinib treatment as planned
 - 1-3.4 g, interrupt the apatinib medication until the 24-hour urine protein is < 1 g, and then resume the apatinib treatment. For the second occurrence, interrupt apatinib treatment until the 24-hour urine protein is < 1 g, and reduce the dose to 250 mg/d. For recurrence after dose reduction, the investigator should evaluate the risks/benefits of the continued apatinib treatment and determine whether the drug should be permanently discontinued
 - ≥ 3.5 g or occurrence of nephrotic syndrome, apatinib treatment is permanently discontinued

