6.4.3 SHR-1210

Dose increase or reduction for SHR-1210 is prohibited. Only interruption or permanent discontinuation is allowed. Dose interruption of SHR-1210 is allowed for up to 8 weeks (from the actual time of last dose); otherwise the treatment of SHR-1210 shall be discontinued. For SHR-1210 interruption that exceeds 8 weeks, the investigator should discuss with the sponsor's medical department if he/she judges that the subjects can benefit from continued treatment.

Refer to [Table 8](#) for the requirements on dose modification of SHR-1210. Refer to Appendix 6 for the guidelines on dose modifications and handling of toxicities of SHR-1210. Refer to [Table 9](#) for the treatment of SHR-1210 related infusion reactions.

In addition, treatment should be discontinued permanently if PD is determined by the investigator as per the RECIST v1.1 criteria (unless subjects meet the criteria for continued treatment after PD as described in Section 6.1.2 of the protocol). For treatment interruption due to medical events, surgeries, or unexpected (holidays) events unrelated to the study treatment, the subject should resume study treatment within 2 weeks after interruption (i.e., originally scheduled administration time), unless otherwise jointly determined by the investigator and the sponsor. The reasons for treatment interruption should be documented in the eCRF.

Table 8. Principles for SHR-1210 dose modification

Adverse Drug Reaction	Severity	Dose Modification
Pneumonia	Grade 2 pneumonia	Treatment interruption ^a
	Grade 3 or 4 pneumonia	Permanent discontinuation
Diarrhea/Enterocolitis	Grade 2 or 3 diarrhea or enterocolitis	Treatment interruption ^a
	Grade 4 diarrhea or enterocolitis	Permanent discontinuation
Dermatitis	Grade 3 dermatitis	Treatment interruption ^a
	Grade 4 dermatitis	Permanent discontinuation
Hepatitis	For subjects with normal baseline ALT, AST, or TBIL, Grade 2 AST, ALT, or TBIL increased, or For subjects with baseline AST, ALT, or TBIL > ULN, AST, ALT, or TBIL increased by ≥ 50% persisting for < 7 days	Treatment interruption ^a
	For subjects with normal baseline ALT, AST, or TBIL, Grade 3 or 4 AST, ALT, or TBIL increased, or For subjects with baseline AST, ALT, or TBIL > ULN, AST, ALT, or TBIL increased by ≥ 50% persisting for ≥ 7 days	Permanent discontinuation
	Grade 2 hypophysitis	Treatment interruption ^b
	Grade 3 or 4 hypophysitis	Permanent discontinuation

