5.3.1 SHR-1210

Compliance (%) = (actual number of doses / scheduled number of doses) \times 100%

Scheduled number of doses = scheduled duration of administration / 14 (days).

The frequency and reasons of SHR-1210 treatment interruption and permanent discontinuation will be summarized.

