5.3.2 Apatinib

Actual dose (tablets): The sum of the documented actual doses of a subject during the treatment period, calculated as the actual number of days of administration \times 1 tablet/day. The actual number of days of administration is subject to the records of apatinib administration. The number of consecutive dosing days for each period is calculated as: end date – start date + 1.

Scheduled dose (tablets): number of treatment cycles during the treatment period \times scheduled number of days of administration \times 1 tablet/day. One treatment cycle contains 28 days.

Apatinib Treatment Cycle	Scheduled Number of Days of Administration in Each Treatment Cycle
QD	28
QD (5 days on, 2 days off)	20
QD (7 days on, 7 days off)	14

Subject compliance (%) = (actual dose / scheduled dose) \times 100%.

The frequency and reasons of apatinib dose reduction, treatment interruption, and permanent discontinuation will be summarized.

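### The dose-reduction criterion for important TEAEs in SAP 5.5.1 names SHR-1210, which may not be reduced, instead of apatinib, which may

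*SAP*

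**What the plan says.** SAP 5.5.1 has important TEAEs summarised by system organ class and preferred term. A TEAE qualifies by any one of three criteria:

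1. "Any TEAE leading to interruption or permanent discontinuation of SHR-1210 or apatinib"
2. "Any TEAE leading to dose reduction of SHR-1210"
3. It was given corrective treatment with a concomitant medication.

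Protocol 6.4.3 sets the rule for SHR-1210: "Dose increase or reduction for SHR-1210 is prohibited. Only interruption or permanent discontinuation is allowed".

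Protocol 6.4.2 sets the rules for apatinib. For several toxicities, Table 7 has the investigator interrupt and, after recovery, "resume the treatment at a reduced dose of 250 mg/d". For a second occurrence of proteinuria in the 1 to 3.4 g range, the text says "interrupt apatinib treatment until the 24-hour urine protein is < 1 g, and reduce the dose to 250 mg/d".

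The exposure sections of the SAP follow the protocol. For apatinib (5.3.2): "The frequency and reasons of apatinib dose reduction, treatment interruption, and permanent discontinuation will be summarized". For SHR-1210 (5.3.1): "The frequency and reasons of SHR-1210 treatment interruption and permanent discontinuation will be summarized".

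**The concern.** Criterion 2 attaches dose reduction to the wrong drug. For SHR-1210 it describes an action that can arise only as a protocol deviation. For apatinib, where reduction is a planned response to toxicity, there is no matching criterion. A programmer who follows the SAP literally would therefore not flag a TEAE as important on the ground that apatinib was reduced.

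This deserves correction because AE incidence is a primary endpoint alongside ORR, because the three groups differ only in the apatinib schedule, and because Protocol 10.5.4 lists dose reduction due to AEs among the safety analyses. What is at stake is whether the important-TEAE summary is complete and agrees with the protocol. ORR and the primary safety endpoint do not depend on it.

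**Working it through.** No arithmetic bears on the definition itself, so the check sets the texts side by side.

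**Step 1: which actions the protocol allows and which the important-TEAE criteria name.**

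| Action | SHR-1210: allowed by protocol | SHR-1210: named in criteria | Apatinib: allowed by protocol | Apatinib: named in criteria |
|---|---|---|---|---|
| Interruption | Yes (6.4.3) | Yes (criterion 1) | Yes (6.4.2) | Yes (criterion 1) |
| Permanent discontinuation | Yes (6.4.3) | Yes (criterion 1) | Yes (6.4.2) | Yes (criterion 1) |
| Dose reduction | No (6.4.3) | **Yes (criterion 2)** | Yes, to 250 mg/d (6.4.2) | **No** |

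The criteria match the protocol for interruption and discontinuation. They are reversed for dose reduction.

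**Step 2: could criterion 2 be met elsewhere under the protocol?** Table 8 and Appendix 6 give only continuation, interruption or permanent discontinuation of SHR-1210. Table 9 allows a slower or paused infusion, which changes the rate and not the dose. Under the protocol as written, the expected number of TEAEs meeting criterion 2 is therefore zero. A reduction made in error remains possible as a deviation.

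**Step 3: do apatinib reductions reach the summary another way?** Protocol 6.4.2 describes five routes to 250 mg/d:

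- hematologic toxicity, Grade 3, second occurrence;
- hematologic toxicity, Grade 4;
- non-hematologic toxicity, Grade 3, second occurrence;
- non-hematologic toxicity, Grade 4;
- proteinuria of 1 to 3.4 g in 24 hours, second occurrence.

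All five require interruption first. If that interruption is recorded against the TEAE, the event meets criterion 1. If corrective treatment was given, it meets criterion 3.

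**Step 4: what is left.** A TEAE is missed only if all of these hold: the sole action recorded for apatinib is dose reduction, criterion 1 is not met through SHR-1210, and no corrective treatment was given. One way this can happen is a toxicity that begins and recovers within scheduled days off apatinib, so that no planned dose is withheld before dosing resumes at the lower level. The dosing days per 28-day cycle in SAP 5.3.2 give the scheduled days off:

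- daily dosing (group A): 28 − 28 = 0;
- 5 days on, 2 off (group B): 28 − 20 = 8;
- 7 days on, 7 off (group C): 28 − 14 = 14.

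This route exists in groups B and C but not in group A.

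**Step 5: are reductions reported elsewhere?** Yes, in two places. SAP 5.3.2 summarises how often apatinib was reduced and why. An earlier part of SAP 5.5.1 includes TEAEs leading to interruption or reduction in the overall table and analyses them separately for each drug. That second analysis pools interruption with reduction, so it does not repair the important-TEAE definition, but it does keep the events in the report.

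**The case against.** The strongest reply is that this is a slip in a summary that largely duplicates others. Most of that reply stands, and it rules out several stronger readings.

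- **That the list leaves apatinib out.** Criterion 1 names it. Only the dose-reduction criterion does not.
- **That a table row will be empty by construction.** The SAP asks for important TEAEs by system organ class and preferred term and does not call for a separate row per criterion. Zero is the expected count for criterion 2, not a logical certainty, because a deviation could produce an event.
- **That anything up to all apatinib reductions could be missed.** This would need every required interruption to go unrecorded against its TEAE and no corrective treatment to be given. Protocol 6.4.1 requires the reasons, actions and results of dose modifications and delays to be recorded in the eCRF. The design of the action-taken field is not in the documents, and nothing there suggests so wide a loss.
- **That the main tolerability comparison between the apatinib schedules is lost.** The primary safety endpoint is AE incidence with listed toxicity categories and does not use dose reduction. Under SAP section 6, the Stage I safety assessment that decides the Stage II groups rests on listings of AEs and laboratory evaluations, not on this summary. Apatinib reductions are also reported in the two places given above.

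None of this makes the criterion correct. It names an action the protocol prohibits, leaves out one the protocol prescribes, and disagrees with SAP 5.3.1 and 5.3.2.

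**Conclusion.** The dose-reduction criterion in SAP 5.5.1 is wrong as written and should be reconciled with Protocol 6.4.2 and 6.4.3 and with SAP 5.3.1 and 5.3.2. Agreement between the protocol and the exposure sections points to a drafting slip rather than a deliberate choice.

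The consequence is minor. It is limited to the important-TEAE summary, and within that to TEAEs recorded only as a reduction of apatinib with no corrective treatment. If interruptions are recorded against the TEAEs that caused them, few or no protocol-specified reductions would be missed. That is an assumption about eCRF recording, and the documents allow no numerical estimate. ORR, the primary safety endpoint and the other reporting of apatinib reductions are unaffected.

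**What to change.** Reword the second important-TEAE criterion in SAP 5.5.1 in one of two ways:

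- *Any TEAE leading to dose reduction of apatinib*. This is the smallest change and matches the actions in SAP 5.3.1 and 5.3.2.
- *Any TEAE leading to dose reduction of SHR-1210 or apatinib*. This parallels criterion 1 and also keeps any SHR-1210 reduction that occurs as a protocol deviation.

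The second is slightly safer, because it loses nothing the present wording would catch. Either costs a few words before database lock and a matching line in the programming specification. No new data are needed, and no dose or clinical rule changes.
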